5.5 Patient Input on Study Design

No patient input was obtained for the study design.

6. Study Population

Investigators will be expected to maintain a screening log of all potential study candidates that includes limited information about the potential candidate (eg, date of screening).

For Cohorts 1-6, eligibility criteria will be evaluated during screening period.

For Cohort 7, eligibility criteria will be evaluated during the screening period. Subjects will not be randomized into a treatment group until after successful completion of the run-in period. Subjects who do not complete the run-in or Part 2 criteria at Day 1 will be removed from study and may be replaced.

Before any study-specific activities/procedures, the appropriate written informed consent must be obtained (see Section 12.3).

Prospective approval of protocol deviations to recruitment and enrollment criteria, also known as protocol waivers or exemptions will not be provided.

6.1 Inclusion Criteria: Part 1

Subjects are eligible to be included in the study only if all of the following criteria apply:

- 101 Subject has provided informed consent prior to initiation of any study specific activities/procedures
- 102 Males and females \geq 18 to \leq 65 years of age, at the time of signing the informed consent

- 103 Capable of giving signed informed consent which includes compliance with the requirements and restrictions listed in the consent form and in the protocol
- 104 Except for obesity, otherwise healthy (or for cohort 7, medically stable as described below) as determined by the investigator or medically qualified designee based on a medical evaluation including medical history, physical examination, laboratory tests, and ECGs on day -2 (cohorts 1, 3, and 5), or day 1 (cohorts 2, 4, and 6), and at screening (cohorts 1-7)

For cohort 7, chronic stable medical conditions that are not otherwise excluded are permitted if in the opinion of the investigator, and the Amgen Medical Monitor if consulted, do not pose a risk to subject safety or interfere with the study evaluation, procedures or completion.

- 105 Body mass index (BMI) between \geq 30.0 kg/m² and \leq 40.0 kg/m²
- 106 Have a stable body weight (less than 5 kg self-reported change during the previous 8 weeks) prior to screening
- 107 Willing to maintain current general diet and physical activity regimen, except for the physical activity in the 72 hours before each blood sample collection for the clinical laboratory analysis, which should not be strenuous
- 108 Female subjects must be of non-reproductive potential (cohorts1-6)

Postmenopausal as defined as:

- Age of ≥ 55 years with no menses for at least 12 months; OR
- Age < 55 with no menses within the past 12 months AND with a follicle-stimulating hormone level > 40 IU/L or according to the definition of "postmenopausal range" for the laboratory involved; OR
- History of hysterectomy; OR
- History of bilateral oophorectomy
- 109 Male subjects must agree to practice an acceptable method of effective birth control while on study through 5 months after receiving study drug. Acceptable methods of effective birth control include sexual abstinence; vasectomy; or a condom with spermicide (males) in combination with barrier methods (diaphragm, cervical cap or cervical sponge), hormonal birth control or IUD (females)
- 110 Male subjects must be willing to abstain from sperm donation while on study through 5 months after receiving study drug
- 111 For cohort 7, currently on liraglutide 3.0 mg SC QD with history of taking liraglutide 3.0 mg SC QD continuously for ≥ 6 months and liraglutide being generally well tolerated per the investigator's discretion (and subjects plan to continue liraglutide 3.0 mg SC QD)

6.2 Exclusion Criteria: Part 1

Subjects are excluded from the study if any of the following criteria apply:

Other Medical Conditions

- History or clinical evidence of diabetes mellitus, including a fasting glucose
 ≥ 125 mg/dl (6.9 mmol/L) and/or HbA1c > 6.5% at screening
- 202 Triglycerides ≥ 5.65 mmol/L (ie, 500 mg/dL) at screening

203	Hepatic liver enzymes ALT, AST, alkaline phosphatase (ALP), or total bilirubin (TBIL) levels > 1.5 (cohorts 1-6) or > 2 (cohort 7) times the upper limit of normal (ULN) at screening
204	History or clinical evidence of bleeding diathesis or any coagulation disorder, including prothrombin time (PT), activated partial thromboplastin time (APTT), International normalized ratio (INR) or platelet count outside of the laboratory's normal reference range at screening
205	Untreated or uncontrolled hypothyroidism/hyperthyroidism defined as thyroid-stimulating hormone > 6 mIU/L or <0.4 mIU/L
206	A corrected QT interval (QTc) at screening of > 450 msec in males or > 470 msec in females or history of long QT syndrome.
207	For cohorts 2, 4, 6, and 7, screening calcitonin \geq 50 ng/L
208	For cohorts 2, 4, 6, and 7 subjects with a family or personal history of medullary thyroid carcinoma or multiple endocrine neoplasia type 2; a personal history of non-familial medullary thyroid carcinoma; confirmed chronic pancreatitis or idiopathic acute pancreatitis, or gallbladder disease (ie, cholelithiasis or cholecystitis) not treated with cholecystectomy
209	Subjects with a history of renal impairment or renal disease and/or estimated glomerular filtration rate (eGFR) \leq 60 mL/min/1.73 m ²
210	Obesity induced by other endocrinologic disorders (eg Cushing's Syndrome)
211	Previous surgical treatment for obesity (excluding liposuction if performed >1 year before trial entry)
212	History of major depressive disorder
213	History of other severe psychiatric disorders, eg schizophrenia, bipolar disorder
214	A patient health questionnaire (PHQ-9) score of ≥ 10
215	Any lifetime history of a suicidal attempt or of any suicidal behavior
216	Any suicidal ideation as identified by endorsement of (answered yes to) any of the items numbered 1-5 on the Columbia Suicide Severity Rating Scale (C-SSRS)
217	Surgery scheduled for the trial duration period, except for minor surgical procedures, at the discretion of the investigator
218	History of malignancy of any type, other than in situ cervical cancer or surgically excised non-melanomatous skin cancers occurring more than 5 years prior to randomization
219	Positive results for human immunodeficiency virus (HIV) antibodies, hepatitis B surface antigen (HBsAg), hepatitis B core antibody (HBcAb), or hepatitis C virus ribonucleic acid (RNA). For hepatitis C, hepatitis C antibody (HepCAb) testing is done at screening, followed by hepatitis C virus RNA by polymerase chain

reaction (PCR) if hepatitis C antibody is positive

- 220 Subject has systolic blood pressure ≥ 150 mm Hg or diastolic blood pressure ≥ 90 mm Hg (cohorts 1-6) or ≥ 95 mm Hg (cohort 7) at screening, or on day -2 (cohorts 1, 3, 5) or day -1 (cohorts 2, 4, 6) or on day -28 (cohort 7). For each visit, if the initial blood pressure is elevated, the reading may be repeated once at least 15 minutes later and the lower of the 2 readings may be used.
- History of myocardial infarction or stroke, or hospitalization for cardiovascular disease in the 6 months prior to screening

Prior/Concomitant Therapy

- 222 Cohorts 1 to 6: Use of the following agents are excluded unless there is a prior consultation between the Principal Investigator and Amgen Medical Monitor:
 - Prescription and nonprescription drugs within 14 days or 5 half-lives, whichever is longer, before the first dose of investigational product, with exception to acetaminophen up to 2 g per day for analgesia, and hormone replacement therapy (eg, estrogen, thyroid)
 - All herbal medicines, vitamins, and supplements consumed by the subject within the 30 days prior to receiving the first dose of investigational product. Exceptions must be reviewed and approved by the investigator and Amgen Medical Monitor
 - Current or history of treatment with medications that may cause significant weight gain, within 3 months prior to screening, including systemic corticosteroids (except for a short course of treatment, ie, 7–10 days), tri-cyclic antidepressants, atypical antipsychotic and mood stabilizers (eg, imipramine, amitriptyline, mirtazapine, paroxetine, phenelzine, chlorpromazine, thioridazine, clozapine, olanzapine, valproic acid and its derivatives, and lithium)
 - Current participation (or within the last 3 months) in an organized weight reduction program or currently using or used within 3 months before screening: pramlintide, sibutramine, orlistat, zonisamide, topiramate, phentermine, naltrexone, bupropion, lorcaserin, or metformin (either by prescription or as part of a clinical trial)

Cohort 7: Use of the following agents are excluded unless there is a prior consultation between the Principal Investigator and Amgen Medical Monitor:

- Current or history of treatment with medications that may cause significant weight gain, within 3 months prior to screening, including systemic corticosteroids (except for a short course of treatment, ie, 7–10 days), tri-cyclic antidepressants, atypical antipsychotic and mood stabilizers (eg, imipramine, amitriptyline, mirtazapine, paroxetine, phenelzine, chlorpromazine, thioridazine, clozapine, olanzapine, valproic acid and its derivatives, and lithium)
- Currently using or used within 3 months before screening including, but not limited to: pramlintide, sibutramine, orlistat, zonisamide, topiramate, phentermine, naltrexone, bupropion, lorcaserin, or metformin (either by prescription or as part of a clinical trial).
- Current participation in diets that include extreme calorie restriction or other activity or dietary practices that cannot be maintained for the duration of trial.

Prior/Concurrent Clinical Study Experience

223 Prior exposure to AMG 598, or currently receiving treatment in another investigational device or drug study, or less than 30 days, or 5 half-lives (whichever is longer), since ending treatment on another investigational device or drug study(ies). Other investigational procedures while participating in this study are excluded

Other Exclusions

- 224 Female subjects who are lactating/breastfeeding or who plan to breastfeed while on study through 5 months after receiving the last dose of investigational product
- 225 Male subjects with partners who are pregnant or planning to become pregnant while the subject is on study through 5 months after receiving the last dose of investigational product
- 226 Female subjects of childbearing potential with a positive pregnancy test assessed at screening (cohort 7) and/or day -1 (cohorts 2, 4, 6) or day -2 (cohorts 1, 3, 5) by a serum pregnancy test and/or urine pregnancy test
- 227 Female subjects (cohort 7) of childbearing potential unwilling to use highly effective method of contraception during treatment and for an additional 5 months after the last dose of AMG598. Refer to Section 12.5 for additional contraceptive information.
- 228 Subject has known sensitivity to AMG 598 or components thereof or a history of drug or other allergy that is in the opinion of the investigator or medical monitor (if appropriate), contraindicates their participation
- 229 Subject has known sensitivity to mammalian derived products
- 230 For cohorts 2, 4, 6 and 7, subject has a known sensitivity to liraglutide or any product components
- 231 Subject likely to not be available to complete all protocol-required study visits or procedures, and/or to comply with all required study procedures to the best of the subject and investigator's knowledge
- 232 Subject has a history or evidence of any other clinically significant disorder, condition or disease (with the exception of those outlined above) that, in the opinion of the investigator or Amgen Medical Monitor, if consulted, would pose a risk to subject safety or interfere with the study evaluation, procedures or completion
- Subject is unwilling or unable to limit alcohol consumption throughout the course of the study. Alcohol is prohibited 48 hours prior to day -2 (cohorts 1, 3, and 5) or day -1 (cohorts 2, 4, 6), day -28 (cohort 7) and is limited to no more than to 2 drinks per day for males and 1 drink per day for females for the duration of the study (1 drink being equivalent to 12 ounces of regular beer, 8 to 9 ounces of malt liquor, 5 ounces of wine, or 1.5 ounces of 80 proof distilled spirits)
- 234 Subject uses nicotine or tobacco containing products (including but not limited to: snuff, chewing tobacco, cigars, cigarettes, e-cigarettes, pipes, or nicotine patches) within 6 months before screening. Subject is unwilling or unable to abstain from nicotine or tobacco, cigars, cigarettes, pipes, or nicotine patches throughout the course of the study
- 235 Subject is tested positive for alcohol and/or drugs of abuse at screening.

- 236 History of substance abuse (ie, alcohol, licit or illicit drugs) within 12 months before screening
- 237 Subject is unwilling to refrain from strenuous exercise (eg, heavy lifting, weight training, and aerobics) for 72 hours prior to each blood collection for clinical laboratory tests
- 238 Subject has donated or lost ≥ 500 mL of blood or plasma within 60 days of day -1

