3.2.2.4 Reproductive and Developmental Toxicity

No nonclinical toxicity studies of the effects of AMG 598 on reproduction and development have been conducted. Females of child-bearing potential may participate in cohort 7 of the study if they are willing to use highly effective method of contraception during treatment and for an additional 5 months after the last dose of AMG 598. AMG 598 is a monoclonal antibody. The embryo-fetal exposure of monoclonal antibodies during organogenesis is understood to be low in humans based on current

CONFIDENTIAL

scientific evidence, and therefore the developmental toxicity study with AMG 598 will be conducted later in drug development (ICH M3 R2, 2009). Male subjects with partners of childbearing potential must practice a highly effective method of birth control for the duration of the study and continuing for 5 months after the last dose of investigational product. Refer to Section 12.5 for additional contraceptive information.

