12.5 Appendix 5. Contraceptive Guidance and Collection of Pregnancy and Lactation Information

Study-specific contraception requirements for males and females of childbearing potential are outlined below.

Male and female subjects of childbearing potential must receive pregnancy prevention counseling and be advised of the risk to the fetus if they become pregnant or father a child during treatment and for 5 months after the last dose of protocol-required therapies.

Definition of Females of Childbearing Potential

A female is considered fertile following menarche and until becoming post-menopausal unless permanently sterile. Permanent sterilization methods include hysterectomy, bilateral salpingectomy, and bilateral oophorectomy.

Females in the following categories are not considered female of childbearing potential:

- Premenopausal female with 1 of the following:
 - Documented hysterectomy;
 - Documented bilateral salpingectomy; or
 - Documented bilateral oophorectomy.

Note: Site personnel documentation from the following sources is acceptable:

1) review of subject's medical records; 2) subject's medical examination; or

3) subject's medical history interview.

- Premenarchal female
- Postmenopausal female
 - A postmenopausal state is defined as no menses for 12 months without an alternative medical cause. A high follicle stimulating hormone (FSH) level in the postmenopausal range may be used to confirm a postmenopausal state in females not using hormonal contraception or hormonal replacement therapy (HRT). However, in the absence of 12 months of amenorrhea, a single FSH measurement is insufficient.
 - Females on HRT and whose menopausal status is in doubt will be required to use 1 of the non-hormonal highly effective contraception methods if they wish to continue their HRT during the study. Otherwise, they must discontinue HRT to allow confirmation of postmenopausal status before study enrollment

Contraception Methods for Female Subjects

Highly Effective Contraceptive Methods

Note: Failure rate of <1% per year when used consistently and correctly.

- Combined (estrogen and progestogen containing) hormonal contraception associated with inhibition of ovulation (oral, intravaginal, or transdermal)
- Progestogen-only hormonal contraception associated with inhibition of ovulation (oral, injectable, implantable)
- Intrauterine device
- Intrauterine hormonal-releasing system
- Bilateral tubal ligation/occlusion

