- Vasectomized partner (provided that partner is the sole sexual partner of the female subject of childbearing potential and that the vasectomized partner has received medical assessment of the surgical success)
- Sexual abstinence (defined as refraining from heterosexual intercourse during the entire period of risk associated with the study treatments; the reliability of sexual abstinence must be evaluated in relation to the duration of the trial and the preferred and usual lifestyle of the subject)

Contraception Methods for Male Subjects

- Sexual abstinence (defined as refraining from heterosexual intercourse during the entire period of risk associated with protocol-required therapies; the reliability of sexual abstinence must be evaluated in relation to the duration of the trial and the preferred and usual lifestyle of the subject)
- Use a condom during treatment and for an additional 5 months after the last dose of protocol-required therapies

The female partner should consider using an acceptable method of effective contraception such as: hormonal, IUD, IUS, female barrier method (diaphragm, cap, sponge [a female condom is not an option because there is a risk of tearing when both partners use a condom]).

Note: If the male's sole female partner is of non-childbearing potential or has had a bilateral tubal ligation/occlusion, he is not required to use additional forms of contraception during the study.

Unacceptable Methods of Birth Control for Male and Female Subjects

Birth control methods that are considered unacceptable in clinical trials include:

- Periodic abstinence (calendar, symptothermal, post-ovulation methods)
- Withdrawal (coitus interruptus)
- Spermicides only
- Lactational amenorrhea method

Collection of Pregnancy Information

Female Subjects Who Become Pregnant

- Investigator will collect pregnancy information on any female subject who becomes pregnant while taking protocol-required therapies through 5 months after last dose of investigational product.
- Information will be recorded on the Pregnancy Notification Worksheet (see Figure 12-2). The worksheet must be submitted to Amgen Global Patient Safety within 24 hours of learning of a subject's pregnancy. (Note: Sites are not required to provide any information on the Pregnancy Notification Worksheet that violates the country or regions local privacy laws).

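### Male contraception: Appendix 5 accepts a condom alone where mandatory criterion 109 lists a condom with spermicide plus a partner method, and the two also differ on vasectomy and partner exemption

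*Protocol*

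**What the plan says.** **Criterion 109.** Section 6.1 opens with "Subjects are eligible to be included in the study only if all of the following criteria apply", and Section 6 rules out waivers. Under 109 a man must agree to effective birth control on study and for 5 months after study drug. The listed methods are abstinence, vasectomy, or "a condom with spermicide (males) in combination with barrier methods (diaphragm, cervical cap or cervical sponge), hormonal birth control or IUD (females".

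**Appendix 5 (Section 12.5).** It begins "Study-specific contraception requirements for males and females of childbearing potential are outlined below". The male list has two items: abstinence, or "Use a condom during treatment and for an additional 5 months after the last dose of protocol-required therapies". It then says "The female partner should consider using an acceptable method of effective contraception", with hormonal methods, IUD, IUS and female barriers as examples. If a man's sole female partner is of non-childbearing potential or has had a tubal ligation or occlusion, "he is not required to use additional forms of contraception during the study".

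**Section 3.2.2.4.** Men with partners of childbearing potential "must practice a highly effective method of birth control for the duration of the study" and for 5 months after the last dose of investigational product. The section points to 12.5 for further information. It also states that AMG 598 has had no reproductive or developmental toxicity studies. The protocol characterises highly effective methods only in the list for female subjects: "Failure rate of <1% per year when used consistently and correctly".

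**Start of the 5 months.** Criteria 109 and 110 and Section 9.2.3.2 count from study drug, without saying last dose. Section 3.2.2.4 and criterion 225 count from the last dose of investigational product. In Appendix 5 the counselling text, the male methods and the partner-pregnancy collection count from protocol-required therapies, while collection for pregnant female subjects ends 5 months after the last investigational product dose.

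The SAP does not touch the subject.

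**The concern.** Site staff can be expected to counsel men from Appendix 5, because that is where the protocol sets out contraception rules and where Section 3.2.2.4 sends them. A man told there that a condom is enough would fall short of what the eligibility criterion lists. With no reproductive toxicity data, contraception is a main safeguard for partners, although Section 3.2.2.4 also says that embryo-fetal exposure to monoclonal antibodies during organogenesis is understood to be low.

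The error can also run the other way. Read literally, criterion 109 makes a man ineligible if he declines its methods because his only partner cannot conceive, though Appendix 5 excuses him. A vasectomised man qualifies under 109 but finds his method missing from the appendix. The mixed wording for the 5 months leaves it less than clear when men's obligations and partner-pregnancy collection end.

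**Working it through.** The plan gives no figure to reproduce here. The main check sets the two operative texts side by side.

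| Man's situation | Criterion 109 | Appendix 5, male section |
|---|---|---|
| Abstinence | Listed | Listed |
| Vasectomy, no condom | Listed | Not listed |
| Condom alone | Not listed | Accepted |
| Condom without spermicide, partner uses a hormonal method | Not listed (no spermicide) | Accepted |
| Condom with spermicide, partner uses barrier, hormonal method or IUD | Listed | Accepted |
| Condom with spermicide, partner uses IUS | IUS not named | Accepted |
| Sole partner non-childbearing or tubal ligation, no method used | No exemption stated | Excused |

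The second and third rows show that neither text is stricter throughout: each admits a man whom the other does not. Taking the overlap is possible, but it would make vasectomised men use condoms and cancel the exemption, and neither document says that is intended. One could read the exemption note as waiving only methods beyond the condom. That would leave it nothing to waive, since the appendix requires nothing beyond the condom.

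Section 3.2.2.4 does not settle the matter. It asks for a highly effective method and refers to 12.5, where the male list applies no such standard.

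**The 5-month anchor.** Inputs:
- Last AMG 598/placebo dose: day 57 (Section 9.1.2).
- Last liraglutide dose: day 84 in cohorts 2, 4 and 6 (Section 9.1.2); day 207 in cohort 7 (synopsis dose table, footnote b).
- Liraglutide is a protocol-required therapy (Section 7.1.4; named as such in Appendix 4).
- Assumption: 5 months = 150 days.

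End of period = last dose day + 150. Extra days = last protocol-required day − 57.

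| Cohorts | Ends, AMG 598/placebo anchor | Ends, protocol-required therapies | Extra days |
|---|---|---|---|
| 1, 3, 5 | 57 + 150 = 207 | 57 + 150 = 207 | 0 |
| 2, 4, 6 | 207 | 84 + 150 = 234 | 84 − 57 = 27 |
| 7 | 207 | 207 + 150 = 357 | 207 − 57 = 150 |

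The extra days do not depend on the length assumed for a month. With the Table 2-3 visit windows (day 57 ± 1, day 207 ± 7), cohort 7 ranges from 200 − 58 = 142 to 214 − 56 = 158. At the half-life of about 27 days in Section 5.4, the shorter period already covers 150 / 27 = 5.6 half-lives, and it ends on the day of the end-of-study visit.

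**The case against.** **Criterion 109 prevails.** It is mandatory and cannot be waived, and a condom user who meets it also meets Appendix 5. This holds for eligibility and for condom users. It does not help with vasectomy or the exemption, and it does not stop a site from giving the weaker advice during the trial.

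**The list in 109 is open, because it says that acceptable methods include those named.** That is a possible reading, but spermicide and a partner method would be pointless conditions if a condom alone sufficed.

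**Whether a man would breach his undertaking depends on the consent form.** That stands. The consent text is not in the documents, so the claim here is limited to what criterion 109 lists.

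Three stronger inferences are tempting, and the documents do not support them.

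- *The anchor wording leaves up to 150 days unprotected.* It does not. Every reading covers about 5 months after the last AMG 598 dose; the 150 days is surplus precaution, in cohort 7 only.
- *The term protocol-required therapies has no settled meaning.* Section 7.1.4, the adverse-event tables in Section 10.3.2.3.2 and Appendix 4 use it consistently to take in liraglutide. Appendix 1 does define Study Day 1 by that term where the SAP uses investigational product. But in cohorts 2, 4 and 6 both products start on day 1, cohorts 1, 3 and 5 have no liraglutide, and Section 9.1.2 sets a separate day 1 rule for cohort 7. The cohort 7 pregnancy-test days fit an AMG 598/placebo reading of Section 9.2.4.1 better, but they concern women and come from a badly extracted table.
- *Criterion 109 itself fails the highly effective standard.* The failure-rate figure sits under female methods. Applying it to men is an inference that only the sponsor can confirm or reject.

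**Conclusion.** The method conflict stands as written. For a condom user, Appendix 5 omits two things that criterion 109 lists: the spermicide and a required partner method. The texts also disagree on vasectomy and on the partner exemption, and Section 3.2.2.4 names a level that the male list does not use. This conclusion rests on the wording alone, plus the reading that 109's list is meant to set the level.

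The anchor is a secondary matter of tidiness: 0, 27 or about 150 extra days by cohort, on the protocol's own classification of liraglutide, with no AMG 598 exposure left uncovered.

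The sponsor should correct this because it alters counselling and eligibility for men. It has no bearing on any endpoint, analysis or sample-size figure, and it gives no ground for holding up the trial.

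**What to change.** State one male contraception rule in Appendix 5 and refer to it from Section 3.2.2.4 and criterion 109.

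- **Level.** By default use 109's: abstinence, vasectomy, or a condom with spermicide together with a required partner method (barrier, hormonal, IUD or IUS). Naming IUS matters, because copying 109 unchanged would drop an option that Appendix 5 now accepts.
- **Exemption.** State it in both criterion 109 and Appendix 5, in the same terms.
- **Confirmation.** The sponsor's safety function should say whether the highly effective standard in Section 3.2.2.4 is meant for men. If it is, the condom-plus-barrier option needs review; if not, Section 3.2.2.4 should be reworded. It should not be lowered by default.
- **Anchor.** Use the last dose of investigational product (AMG 598/placebo) in criteria 109 and 110, Section 9.2.3.2 and the male parts of Appendix 5. This matches the meaning already used in Section 3.2.2.4 and criterion 225.

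The cost is amendment and consent wording, IRB/IEC review where necessary and re-consent to the current form, as Appendix 3 requires. It is best bundled with the next amendment. Visits, data collection and analyses do not change.
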